1.2 Study Organization

The name and contact information of the responsible party and individuals involved with the study (eg, investigator(s), sponsor's medical expert and study monitor, sponsor's representative(s), laboratories, steering committees, and oversight committees [including ethics committees (ECs)], as applicable) will be maintained by the sponsor and provided to the investigator.

2. SERIOUS ADVERSE EVENT REPORTING

The investigator will comply with applicable laws/requirements for reporting serious adverse events (SAEs) to the ECs.

**ALL SAEs ARE TO BE REPORTED ON THE
SERIOUS ADVERSE EVENT REPORT (SAER) FORM AND
TRANSMITTED TO THE SPONSOR
WITHIN 24 HOURS AFTER BECOMING AWARE OF THE EVENT**

**See SAER form for contact information.
Further details are also available in the study team roster.**

For definitions and information on the assessment of these events, refer to the following:

- AE, Section [12.1](#)
- SAE, Section [12.1.1.1](#)
- Assessment of AEs, Section [12.1.2](#)

3. SYNOPSIS

INVESTIGATIONAL PRODUCT	
Name of Investigational Product (IP)	BAX 855
Name(s) of Active Ingredient(s)	PEGylated recombinant factor VIII (PEG-rFVIII)
CLINICAL CONDITION(S)/INDICATION(S)	

 Previously treated patients (PTPs) with severe hemophilia A (FVIII <1%) 	
PROTOCOL ID	261302
PROTOCOL TITLE	A Phase 3b Continuation study of the Safety and Efficacy of PEGylated Recombinant Factor VIII (PEG-rFVIII; BAX 855) in Prophylaxis of Bleeding in Previously Treated Patients with Severe Hemophilia A
Short Title	BAX 855 Continuation
STUDY PHASE	Phase 3b
PLANNED STUDY PERIOD	
Initiation	2013 OCT
Primary Completion	2017 Q4
Study Completion	2017 Q4
Duration	The overall duration of the study is estimated to be approximately 4 years from study initiation to last subject last visit.
STUDY OBJECTIVES AND PURPOSE	
Study Purpose	

 To continue the evaluation of the safety and efficacy of BAX 855 for prophylaxis and treatment of bleeding episodes in adult and pediatric PTPs aged ≤ 75 years of age with severe hemophilia A. 	
Primary Objective	
The co-primary objectives of the study are: 
 To determine the safety of BAX 855 based on the incidence of FVIII inhibitory antibody development To determine the efficacy of BAX 855 based on the annualized bleed rate (ABR) of spontaneous bleeding episodes 	
Secondary Objective(s)	
Efficacy	

 To determine the total ABR (spontaneous and traumatic bleeding episodes) To determine the overall hemostatic efficacy rating of BAX 855 for treatment of breakthrough bleeding episodes To determine the length of intervals between bleeding episodes To characterize the hemostatic efficacy of BAX 855 for treatment of bleeding episodes by the number of BAX 855 infusions for treatment To determine total weight-adjusted consumption of BAX 855 for prophylaxis and for treatment of bleeding episodes To assess Patient Reported Outcomes (PROs) over time for subjects receiving BAX 855 	

Safety	

 To determine the safety of BAX 855, as assessed by the occurrence of adverse events (AEs) and changes in vital signs and clinical laboratory parameters To determine the immunogenicity of BAX 855 	
Exploratory Objective	

 To assess patient satisfaction, patient activity levels, and health resource use over time for subjects receiving BAX 855 To determine the potential correlation between thrombin generation assay (TGA) parameters, FVIII trough levels and ABR 	
STUDY DESIGN	
Study Type/ Classification/ Discipline	Safety and Efficacy
Control Type	No Control
Study Indication Type	Prevention and Treatment
Intervention model	Parallel
Blinding/Masking	Open-label
Study Design	
This is a phase 3b, prospective, open label, multi-center study to evaluate the safety and efficacy of BAX 855 for prophylactic use and the control of bleeding episodes in approximately 200 pediatric and adult PTPs ≤ 75 years of age with severe hemophilia A. The study plans to include subjects from other BAX 855 studies and BAX 855-naïve subjects.
 
Subjects will receive either a fixed dose prophylaxis with BAX 855 consisting of 45 ± 5 IU/kg for subjects aged ≥ 12 years or 50 ± 10 IU/kg for subjects aged < 12 years twice weekly or, subjects can decide to receive a pharmacokinetically-tailored (PK-tailored) prophylactic BAX 855 dosing regimen based on the subject's individual PK to maintain FVIII trough levels of $\geq 3\%$. The frequency of PK-tailored prophylactic BAX 855 dosing will be at least twice weekly.

Planned Duration of Subject Participation	
Each subject will participate in the study until a total of at least 100 exposure days (EDs) to BAX 855 has been achieved (accumulated across all BAX 855 studies in which each subject participated).
 
Depending on the subject's BAX 855 exposure history and treatment regimen given, the planned duration of subject participation to reach the 100 EDs can vary from approximately 3 to 12 months. However, extension of the study duration for individual subjects beyond the 100 EDs may be granted.

Primary Outcome Measure	

Safety: Development of inhibitory antibodies to FVIII
 
Efficacy: Spontaneous ABR
	
Secondary Outcome Measure(s)	

Efficacy
 
 Total ABR (spontaneous and traumatic bleeding episodes) Overall hemostatic efficacy rating of BAX 855 for treatment of breakthrough bleeding episodes Number of BAX 855 infusions to treat bleeding episodes 	


4. Time intervals between bleeding episodes
 
5. Weight-adjusted consumption of BAX 855
 
Safety
 
1. Occurrence of AEs and serious adverse events (SAEs)
 
2. Changes in vital signs and clinical laboratory parameters (hematology, clinical chemistry, and lipids)
 
3. Immunogenicity
 
a. Binding antibodies (IgG and IgM) to FVIII, BAX 855, and PEG
 
b. Anti-Chinese hamster ovary (CHO) antibodies
 
Patient Reported Outcomes (PROs)
 
Changes from baseline in parent study, if applicable, in the following:
 
1. Bleed and pain severity as measured using the Haemo-SYM questionnaire
 
2. Health-related quality of life (HRQoL) as assessed using the SF-36/PedsQL questionnaires
	
Exploratory Outcome Measure(s)	

1. Patient satisfaction with treatment will be assessed using the Satisfaction Question Set
 
2. Patient Activity Level
 
3. Health resource use data (eg, physician office visits, hospitalizations, days missed from work/school)
 
4. TGA parameters, FVIII trough levels and ABR
	
INVESTIGATIONAL PRODUCT(S), DOSE AND MODE OF ADMINISTRATION	
Active Product	
BAX 855
 
Dosage form: injection, powder, lyophilized, for solution.
 
Dosage frequency:
 
 • Fixed prophylactic regimen: 
 ○ Subjects aged ≥ 12 years: 45 ± 5 IU/kg twice weekly, which may be increased up to 80 IU/kg ○ Subjects aged < 12 years: 50 ± 10 IU/kg twice weekly, which may be increased up to 80 IU/kg 
OR
 
 • PK-tailored prophylactic BAX 855 regimen based on subject's individual PK profile to maintain a FVIII trough level of $\geq 3\%$. However, the dosing regimen should not exceed 80 IU/kg for any single infusion and the FVIII peak levels should not exceed 200%. 
Mode of Administration: intravenous bolus infusion

SUBJECT SELECTION	
Targeted Accrual	Approximately 250 PTPs with severe hemophilia A.
Number of Groups/Arms/Cohorts	Two: Fixed BAX 855 prophylaxis or PK-tailored BAX 855 prophylaxis

Inclusion Criteria

Subjects transitioning from other BAX 855 studies

Subjects transitioning from other BAX 855 studies who meet **ALL** of the following criteria are eligible for this study:

1. Subject has completed a previous BAX 855 study and is willing to immediately transition into this continuation study.ⁱ
2. Subject is ≤ 75 years of age at screening of the previous BAX 855 study.
3. Subject continues to have a Karnofsky (for subjects aged ≥ 16 years) or Lansky (for subjects aged < 16 years) performance score of ≥ 60 (see Section 20.5).
4. Subject is human immunodeficiency virus negative (HIV-); or HIV+ with stable disease and CD4+ count ≥ 200 cells/mm³, as confirmed by central laboratory at screening.
5. Subject is hepatitis C virus negative (HCV-) by antibody or PCR testing (if positive, antibody titer will be confirmed by PCR), as confirmed by central laboratory at screening; or HCV+ with chronic stable hepatitis.
6. If female of childbearing potential, subject presents with a negative urine pregnancy test and agrees to employ adequate birth control measures for the duration of the study.
7. Subject and/or legally authorized representative is willing and able to comply with the requirements of the protocol.

BAX 855 naïve subjects

BAX 855 naïve subjects who are ≥ 12 years of age can only be enrolled in this continuation study after enrollment in the phase 2/3 pivotal study is closed. BAX 855 naïve subjects who are < 12 years of age can only be enrolled in this continuation study after enrollment in the pediatric PTP study is closed.

Enrolment of BAX 855 naïve subjects will only start once the sponsor has notified the study sites accordingly.

BAX 855 naïve subjects who meet **ALL** of the following criteria are eligible for this study:

1. Subject is ≤ 75 years of age at screening.
2. Subject is naïve to BAX 855.
3. Subject has severe hemophilia A (FVIII clotting activity $< 1\%$) as confirmed by central laboratory at screening after at least a 72-hour washout period.ⁱⁱ
4. Subject aged ≥ 6 years has documented previous treatment with plasma-derived FVIII concentrates or rFVIII for ≥ 150 EDs.
5. Subject aged < 6 years has documented previous treatment with plasma-derived FVIII concentrates or rFVIII for ≥ 50 EDs.
6. Subject is currently receiving prophylaxis or on-demand therapy with FVIII.

ⁱ NOTE: Subjects who have received FVIII concentrates other than BAX 855 following completion of the previous BAX 855 study are excluded from participation in this continuation study.

ⁱⁱ If FVIII activity is $\geq 1\%$, severe hemophilia A classification can be confirmed by historically documented FVIII clotting activity $< 1\%$ performed by a certified clinical laboratory or by a documented genotype known to result in severe hemophilia A.

7. Subject has a Karnofsky (for subjects aged ≥ 16 years) or Lansky (for subjects aged < 16 years) performance score of ≥ 60 (see Section 20.5).
8. Subject is HIV-; or HIV+ with stable disease and CD4+ count ≥ 200 cells/mm³, as confirmed by central laboratory at screening.
9. Subject is HCV- by antibody or PCR testing (if positive, antibody titer will be confirmed by PCR), as confirmed by central laboratory at screening; or HCV+ with chronic stable hepatitis.
10. If female of childbearing potential, subject presents with a negative urine pregnancy test and agrees to employ adequate birth control measures for the duration of the study.
11. Subject and/or legally authorized representative is willing and able to comply with the requirements of the protocol.

Exclusion Criteria

Subjects transitioning from other BAX 855 studies

Subjects transitioning from other BAX 855 studies who meet **ANY** of the following criteria are not eligible for this study:

1. Subject had detectable FVIII inhibitory antibodies (≥ 0.6 BU using the Nijmegen modification of the Bethesda assay) as confirmed by central laboratory at screening.
2. Subject has developed FVIII inhibitory antibodies (≥ 0.6 BU using the Nijmegen modification of the Bethesda assay as determined at central laboratory in a previous BAX 855 study).
3. Subject has acquired a hemostatic defect other than hemophilia A (eg, qualitative platelet defect or von Willebrand's disease) in a previous BAX 855 study.
4. Subject has severe chronic hepatic dysfunction (eg, ≥ 5 times upper limit of normal alanine aminotransferase [ALT], as confirmed by central laboratory at screening).
5. Subject has severe renal impairment (serum creatinine > 2.0 mg/dL), as confirmed by central laboratory at screening.
6. Subject experienced a life-threatening or gastrointestinal bleeding episode within 3 months prior to study entry.
7. Subject is scheduled to use other PEGylated drugs during study participation.
8. Subject is planning to take part in any other clinical study during the course of the continuation study, with the exception of any other parallel BAX 855 study.
9. Subject has medical, psychiatric, or cognitive illness or recreational drug/alcohol use that, in the opinion of the investigator, would affect subject safety or compliance.
10. Subject is a family member or employee of the investigator.

BAX 855 naïve subjects

BAX 855 naïve subjects who meet **ANY** of the following criteria are not eligible for this study:

1. Subject has detectable FVIII inhibitory antibodies (≥ 0.6 BU using the Nijmegen modification of the Bethesda assay) as confirmed by central laboratory at screening.
2. Subject has history of FVIII inhibitory antibodies (≥ 0.6 BU using the Nijmegen modification of the Bethesda assay or the Bethesda assay) at any time prior to screening.
3. Subject has been diagnosed with an inherited or acquired hemostatic defect other than hemophilia A (eg, qualitative platelet defect or von Willebrand's disease).
4. Subject has known hypersensitivity towards mouse or hamster proteins, PEG, or Tween 80.

5. Subject has severe chronic hepatic dysfunction (eg, ≥ 5 times upper limit of normal ALT, as confirmed by central laboratory at screening).
6. Subject has severe renal impairment (serum creatinine > 2.0 mg/dL), as confirmed by central laboratory at screening.
7. Subject experienced a life-threatening or gastrointestinal bleeding episode within 3 months prior to study entry.
8. Subject has current or recent (< 30 days) use of other PEGylated drugs prior to study participation or scheduled use of such drugs during study participation.
9. Subject has participated in another clinical study involving an IP other than BAX 855 or device within 30 days prior to enrollment or is scheduled to participate in another clinical study involving an IP or investigational device during the course of this study.
10. Subject has medical, psychiatric, or cognitive illness or recreational drug/alcohol use that, in the opinion of the investigator, would affect subject safety or compliance.
11. Subject is a family member or employee of the investigator.

STATISTICAL ANALYSIS

Sample Size Calculation

In total, approximately 250 subjects will be enrolled in this study. This sample size is based on having 200 evaluable subjects with a minimum of 100 EDs to BAX 855 in accordance with the guidance EMA/CHMP/BPWP/144533/2009.

Planned Statistical Analysis

Analysis of Primary Outcome Measures

Safety:

The number and proportion (Clopper-Pearson exact 95% CI) of subjects having been exposed to BAX 855 who develop inhibitory antibodies to FVIII (≥ 0.6 BU) will be provided.

Efficacy:

The spontaneous ABR will be assumed to have a negative binomial distribution, and the mean ABR (95% CI) will be estimated using a general estimating equation (GEE) model framework (with a logarithmic link function which is the default for the negative binomial distribution) with treatment regimen as a fixed effect, subject effect as a random effect, age at baseline as a continuous covariate, and the logarithm of follow-up time (in years) as an offset.

Analysis of Secondary Outcome Measures

Efficacy:

The total ABR (spontaneous and traumatic bleedings) will be estimated and described similarly as the primary efficacy outcome measure.

The efficacy of BAX 855 in the treatment of bleeds will be summarized. It includes overall hemostatic efficacy rating at 24 (± 2) hours after initiation of treatment and at resolution of bleed, number of BAX 855 infusions to control bleeding and total weight-adjusted dose per bleeding episode (excluding any infusions given to maintain hemostasis after the bleeding was controlled), and time interval between bleeding episodes.

Frequency tables will be prepared for the number of BAX 855 infusions required for the treatment of bleeding episodes. The median number of infusions (and nonparametric 95% CI) will be estimated.

Weight-adjusted consumption of BAX 855 for prophylaxis, treating bleeding episodes (excluding any infusions given to maintain hemostasis after the bleeding is controlled) and in total per subject will be summarized separately as average number of BAX 855 infusions and average weight-adjusted consumption of BAX 855 per month.

The average time interval between 2 consecutive bleeding episodes will be computed for each subject as the duration of the observation period divided by the number of bleeding episodes in the observation period. The median (95% CI) of those average time intervals between 2 bleeding episodes will be estimated.

Pharmacokinetics:

For subjects undergoing a pharmacokinetic (PK) assessment in this study, the following PK parameters for FVIII will be reported using descriptive statistics: area under the plasma concentration curve from 0 to infinity ($AUC_{0-\infty}$), half-life ($T_{1/2}$), mean residence time (MRT), total body clearance (CL), incremental recovery over time (IR), maximal plasma concentration (C_{max}), and volume of distribution at steady state (V_{ss}).

For subjects undergoing a PK assessment in this study, an exploratory analysis of correlation of baseline von Willebrand factor (VWF) antigen to BAX 855 PK will be performed as well as the possible influence of any anti-PEG antibodies (preexisting or detected during study participation) on the PK of BAX 855, if applicable.

IR will be summarized by visit and displayed graphically over time for each subject. Also the change from the baseline will be described using summary statistics.

Safety:

Frequency counts and percentages will be calculated for SAEs, occurrence of inhibitory antibodies to FVIII, occurrence of binding antibodies to FVIII, BAX 855, PEG, occurrence of anti-CHO antibodies, occurrence of severe allergic reactions, and occurrence of thrombotic events.

AEs that occurred during or after treatment will be presented in summary tables. AEs will be cross-tabulated for relatedness, seriousness, and severity. AEs will be categorized according to the MedDRA dictionary and summarized by system organ class and preferred term.

Vital signs and laboratory parameters will be characterized descriptively. Shift tables will be prepared for laboratory parameters. Clinically significant abnormal values in routine laboratory parameters (hematology, clinical chemistry, lipids) and vital signs will be summarized.

Patient Reported Outcomes (PROs):

Bleed and pain severity will be measured using the Haemo-SYM questionnaire with higher scores on the Haemo-SYM indicating more severe symptoms. Changes from baseline in the Haemo-SYM scores will be tested for statistical significance using a Wilcoxon test for paired samples. Number and proportion of subjects with an improvement in the Haemo-SYM pain subscale will be tabulated.

HRQoL will be measured using the SF-36 questionnaire with lower scores on SF-36 indicating worse HRQoL. Changes from baseline in the SF-36 scores will be tested for statistical significance using a Wilcoxon test for paired samples. The number and proportion of subjects with an improvement in SF-36 will be tabulated.

HRQoL in subjects aged < 14 years will be measured using the PedsQL with lower scores on the PedsQL indicating worse HRQoL. Changes from baseline to end of study in the PedsQL scores will be tested for statistical significance using a Wilcoxon test for paired samples. Number and proportion of subjects with an improvement in the PedsQL will be tabulated.

Analysis of Exploratory Outcome Measures

Patient satisfaction with treatment, patient activity level and health resource use data will be descriptively summarized and listed.

TGA parameters (lag time, time to peak thrombin generation, peak thrombin generation, and endogenous thrombin potential [ETP]) will be presented descriptively and displayed graphically. The potential influence of TGA parameters and FVIII trough levels on ABR in the three months after TGA/FVIII trough level measurement will be explored by scatterplots where TGA is performed.

Interim Safety Reviews

A first interim safety review will be performed for marketing authorization application to the European Medicines Agency (EMA).

If applicable, a second interim safety review may be performed once 200 subjects have accumulated at least 100 EDs to BAX 855.

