Subjects receiving a PK-tailored prophylactic treatment regimen will have their PK assessment performed following eligibility confirmation. Following PK assessment, they undergo their baseline visit and subsequent visits every 3 months following their baseline visit for IR determination, efficacy and safety assessment and e-diary review. In addition, at 4, 8 and 18 weeks after the baseline visit, subjects' FVIII levels, TGA parameters and VWF antigen will be measured to ensure that FVIII trough levels of $\geq 3\%$ are maintained, and, if necessary, dose adjustments will have to be performed. Also, hemostatic efficacy and clinical safety will be assessed and e-diary reviewed.

Investigators will review e-diaries for untoward events, concomitant medications, non-drug therapies, and patient reported outcomes (PROs; see Section 10.5.2). Safety assessments performed at the study visit will include immunogenicity (inhibitory antibodies for FVIII and binding antibodies for FVIII, BAX 855, PEG, and CHO), and changes in conditions of the physical examination, vital signs, and clinical laboratory assessments (hematology, clinical chemistry, and lipids). Subjects who develop a high responder inhibitor (> 5 Bethesda Units [BU]), or who develop a low responder inhibitor (≤ 5 BU but ≥ 0.6 BU) that cannot be adequately managed by the prescribed prophylaxis regimen with BAX 855 will be discontinued from study. At every study visitⁱⁱⁱ, IR for FVIII activity and TGA parameters (optional in subjects receiving fixed dose prophylaxis) will be determined within 30 minutes prior to infusion with 60 ± 5 IU/kg BAX 855 and 30 ± 15 minutes following the infusion. Also, TGA parameters and pre-infusion VWF antigen level will be assessed in subjects receiving a PK-tailored dosing (optional for subjects aged < 12 years).

The sponsor will suspend enrollment and treatment if 2 or more subjects develop anaphylaxis after BAX 855 treatment. The sponsor may stop this study at any time. In addition, the sponsor may modify the study based on results of the other BAX 855 studies.

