- One or more spontaneous (not trauma-related) bleeding episodes in a non-target joint within any 2-month period
- FVIII trough level < 3%

The BAX 855 dosage may be increased gradually up to a maximum of 80 ± 5 IU/kg and/or the dosing frequency may be increased, in case the subject continues to experience spontaneous breakthrough bleeding episodes. In any case, the sponsor should be notified if any of the above criteria are met and dose/frequency adjustment is performed; dose/frequency adjustment options can be discussed with the sponsor's medical director.

Additionally, subjects with severe hemophilic arthropathy and/or target joints who continue to experience recurrent bleeding episodes despite adjustments to the prophylactic dose and/or dosing frequency, an ultrasound of the affected joint(s) should be performed to verify the presence of a bleed.

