13.4.6 Exploratory Outcome Measures

Patient satisfaction with treatment, patient activity level and health resource use data will be descriptively summarized and listed.

The potential influence of TGA parameters and FVIII trough levels on ABR in the three months after TGA/FVIII trough level measurement will be explored by scatterplots for all subjects who have TGA tested.

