 - Review bleeding episodes and their treatment
 - Adverse events
 - Concomitant medications and non-drug therapies
- Laboratory assessments within 30 minutes of start of infusion:
 - FVIII activity and antigen
 - TGA parameters and VWF antigen (optional in subjects aged < 12 years)
- Vital signs (within 15 minutes of IP infusion)

Infusion of the PK-tailored prophylactic dose of BAX 855

Other procedures:

- Dispense IP:
 - A sufficient quantity of IP will be dispensed to cover the period until the next scheduled visit
- Upon availability of the FVIII trough levels dose adjustments, if applicable

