# 10.5 TGA Parameters, FVIII Trough Levels, Incremental Recovery and Comparisons against ABR

PK concentrations are to be obtained from the central laboratory and PK parameters based on the PK concentrations are to be derived by Baxalta. Further details on the calculation of PK parameters are to be documented separately.

PK concentrations and PK parameters for all analytes are to be summarized and listed for the PKAS.

Incremental recovery (IR) as derived below will be summarized for the SAF by visit including changes from baseline. IR will also be displayed graphically over time for each subject. All IR results will be reviewed by the medical team for plausibility. All IR results found not plausible by the medical team will be excluded from the analysis.

The following formula will be used to determine IR:

$$IR[(IU/dL)/(IU/kg)] = \frac{PostFVIII [IU/dL] - PreFVIII [IU/dL]}{Weight Adjusted Dose [IU/kg]}$$

where *PreFVIII* is the last available FVIII measurement prior to dose and *PostFVIII* the first FVIII measurement after dose.

FVIII trough levels and TGA results per subject are to be plotted in a scatter plot against the ABR of the three months after FVIII trough level and TGA measurement with a regression line overlaid on the individual points. The ABR of the three months after FVIII trough level and TGA measurement will be determined as described in Section 7.1: Bleeding Episodes and by counting the bleeds to the next scheduled visit (which is scheduled every three months).

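### In the PK-tailored regimen a low trough can lead to a dose or frequency increase inside the window whose bleeds are plotted against that trough, so the exploratory trough–ABR relation is attenuated toward null

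*Protocol*

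**What the plan says.** The second exploratory objective (Protocol 7.4, SAP 1.1.3) is the possible correlation between TGA parameters, FVIII trough and ABR. The synopsis pairs each measurement with later bleeding: "FVIII trough levels on ABR in the three months after TGA/FVIII trough level measurement will be explored by scatterplots where TGA is performed". Protocol 13.4.6 repeats this with slightly different wording: the relation "will be explored by scatterplots for all subjects who have TGA tested". SAP 10.5 specifies the output: "FVIII trough levels and TGA results per subject are to be plotted in a scatter plot against the ABR of the three months after" the measurement, "with a regression line overlaid on the individual points". It obtains the bleeds "by counting the bleeds to the next scheduled visit (which is scheduled every three months").

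The same trough guides treatment in the PK-tailored regimen:

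- Protocol 8.2 schedules trough checks at weeks 4, 8 and 18 so that levels stay at or above 3%, and "if necessary, dose adjustments will have to be performed".
- Protocol 8.7.3.4 lists three criteria, any one of which may lead to a higher dose or frequency. Two are spontaneous joint bleeds. The third is "FVIII trough level < 3"%.
- Protocol 20.2.2.4 puts the timing in the visit procedures: "Upon availability of the FVIII trough levels dose adjustments, if applicable".

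SAP 7.1 derives ABR separately for each treatment regimen. Neither document ends, splits or marks the post-measurement window when dose or frequency changes within a regimen.

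**The concern.** The x-value can change the exposure during its own outcome period, and as a trough-driven change this happens only at the low end of the axis. A PK-tailored subject measured at 2% may be moved to a higher trough within the window, yet all bleeds in the window are plotted at 2%. A subject measured at 5% is not adjusted on account of the trough. The misclassification is therefore systematic: it lowers the bleeding rate shown at low troughs and flattens the line.

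The plotted set leans toward the subjects affected. Protocol 13.4.6 restricts the plot to subjects with TGA, and Protocol 12.7.5 makes TGA optional in the fixed-dose regimen and in PK-tailored subjects under 12. The split by regimen in SAP 7.1 may separate a switch from fixed to PK-tailored dosing, but not an increase within the PK-tailored regimen.

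At stake is how the plot can be read. A shallow line could reflect a weak relation or the adjustment of low troughs, and the planned output cannot tell these apart.

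**Working it through.** The plan gives no slope, correlation or sample size for this analysis, so there is no figure to reproduce. The check concerns the direction of the bias and a plausible range for its size.

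**From the documents.** The trough criterion is below 3% (8.7.3.4). Adjustment follows availability of the result (20.2.2.4), with no lag stated. The window is three months (synopsis), or runs to the next scheduled visit (SAP 10.5). PK-tailored visits fall at weeks 4, 8 and 18 and every 3 months, about weeks 13 and 26. The gaps are therefore 8 − 4 = 4, 13 − 8 = 5, 18 − 13 = 5 and 26 − 18 = 8 weeks.

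**Assumed.** ABR is 4 per year at a 1% trough, with rate ratio (RR) 0.70 or 0.85 per additional 1%. Troughs are lognormal with median 3.5% and CV 0.6, with between-subject variation in rate. The share of low troughs adjusted is 25%, 50% or 100%. The lag L is 1, 2 or 4 weeks in a window W of 13 weeks, or 2 weeks in a window of 4, 5 or 8 weeks. An adjusted subject moves at once to 3.0% or 4.5%.

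**Formula.** With rate r(t) = 4 × RR^(t − 1), an adjusted subject's expected window ABR is r(t) × L/W + r(t′) × (1 − L/W), where t′ is the trough after adjustment.

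**One point by hand** (RR 0.70, measured 2%, adjusted to 3%, L = 2, W = 13):

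- r(2) = 4 × 0.70 = 2.80 and r(3) = 4 × 0.49 = 1.96.
- Expected ABR = 2.80 × 2/13 + 1.96 × 11/13 = 0.43 + 1.66 = 2.09, plotted at 2%.
- Against a subject at 4%, r(4) = 4 × 0.343 = 1.37. The contrast is 2.09 − 1.37 = 0.72 instead of 2.80 − 1.37 = 1.43, so about half is kept.
- With W = 4 the expected ABR is (2.80 + 1.96)/2 = 2.38, and the contrast is 1.01, about 71%.

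**Slope over the whole plot.** The least-squares slope with adjustment was divided by the slope without it, using 400,000 simulated subjects per scenario. For W = 13 and L = 2:

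| Low troughs adjusted | RR 0.70, to 3.0% | RR 0.70, to 4.5% | RR 0.85, to 3.0% | RR 0.85, to 4.5% |
|---|---|---|---|---|
| 25% | 0.93 | 0.86 | 0.95 | 0.90 |
| 50% | 0.85 | 0.73 | 0.90 | 0.79 |
| 100% | 0.71 | 0.45 | 0.81 | 0.59 |

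There were 2 × 3 × 6 × 2 = 72 PK-tailored scenarios (RRs, shares, lag and window pairs, post-adjustment troughs). The slope was attenuated in every one and never reversed, keeping 40% to 97%. With windows of 4 to 8 weeks and all low troughs adjusted, 52% to 89% remained. Under a fixed-dose type rule (below 1%, assumed median trough 2%), 89% to 97% remained.

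**Does stopping at the change help?** The simulation above contains no bleed-prompted changes, so it cannot answer this. In a separate simulation with gamma frailty, a negative binomial model used bleeds up to the first change with log observed time as offset. Its log-rate slope was 0.97 to 1.04 of the true value, even when every first bleed led to a change. The same model on full windows gave 0.55 to 0.93.

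**The case against.** **Adjustment is not automatic.** A reader might infer that every low trough triggers an increase and that low-trough points show wholly the bleeding rate of a corrected trough. The documents do not say so. Protocol 8.7.3.4 is permissive, speaks of gradual increases up to a maximum, and links them to continued spontaneous bleeding. Sections 8.2 and 20.2.2.4 are conditional. In the fixed-dose regimen (8.7.3.2) a trough below 1% counts only together with the investigator's view that bleeding risk is raised. This stands: the points are mixtures, and the share adjusted is unknown.

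**A simple formula exaggerates the loss.** With a share p adjusted, 1 − p(1 − L/W) at p = 1, L = 2 and W = 13 gives 1 − 11/13 = 15% retained. That describes a two-group contrast in which adjustment at once removes the whole difference. The planned output is a line, which keeps 45% to 81% in the same setting (last row of the table). With next-visit windows of 4, 5 or 8 weeks, even this formula gives 50%, 40% or 25%. The objection stands against the larger figures but not against the direction.

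**Truncation depends on the outcome.** Spontaneous bleeds also prompt changes, so stopping at a change can shorten a window because a bleed occurred. In a worst case (13-week window, every first bleed followed by a change 2 weeks later, true ABR 1 to 4), the mean ABR of truncated points was inflated 1.6- to 1.9-fold. With gamma heterogeneity the pooled rate fell 8% to 20% below truth. This rules out plotting annualised truncated ABRs as comparable points, and it counsels against reading absolute rates from the truncated model. The model's slope was nevertheless close to truth.

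**It is only an exploratory plot.** No test or decision rests on it, the regimen is chosen by the subject, and Protocol 6.1 supports the 3% target from literature. A reader might infer that the plot is the trial's test of that target; no section makes it so. That limits the importance, but a line drawn through the points will still be read as the relation.

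**Conclusion.** The concern holds for the PK-tailored regimen. Following SAP 10.5 as written attenuates the trough–ABR relation, and nothing in either document removes this. The direction rests on two things: higher troughs going with fewer bleeds, and some low troughs being raised within the window. The size is not derivable, because the lag, the share adjusted and the trough distribution are not given; 40% to 97% of the slope retained is a range over stated assumptions, not an estimate for this trial. A gradual rise in trough, or few adjustments, would put the loss at the small end. Repeat troughs after adjustment add new points but do not correct the earlier ones. A flat or shallow line should not be taken as evidence of no relation. The co-primary outcomes, inhibitor development and spontaneous ABR, are not touched.

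**What to change.** Amend SAP 10.5 and bring Protocol 13.4.6 into line:

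1. Keep the scatterplot, but mark points whose dose or frequency changed within the window, using the Change of Treatment Assignment eCRF (SAP 6.7). Do not plot ABRs annualised from truncated windows beside full-window ABRs as if comparable.
2. Replace the overlaid line, as the summary of the relation, with the negative binomial GEE of SAP 7.1. Use bleeds up to the first dose or frequency change, log observed time as offset, subject as cluster, and trough or TGA value as covariate. Report the rate ratio with its 95% CI.
3. Add a sensitivity analysis that ends the window only at changes not prompted by a bleed. Protocol 8.7.3.4 already asks that the sponsor be notified when a criterion is met and an adjustment is made, so the reason should be traceable. If it is not coded, define a rule before database lock.
4. State one window. Three months and the next scheduled visit differ for PK-tailored subjects, who are also seen at weeks 4, 8 and 18.

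The cost is SAP wording and a small program on data already collected. Some windows become shorter, and low-trough subjects then contribute less time and less precision. If the model is not adopted, marking the points and stating the limitation beside the plot is the minimum.
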